3.4 CONCURRENT THERAPIES

This study allows blood and stool procurement before, during, and after patients receive radiation therapy. It is possible that patients may also be treated with neoadjuvant, concurrent, or adjuvant

chemotherapy. Patients may also receive surgery as part of definitive therapy. This is allowed but protocol enrollment and the initial sample collection must occur prior to initiation of chemotherapy or complete resection.

3.5 RADIATION THERAPY GUIDELINES

This is not a study of an experimental therapy. It is to be performed in conjunction with protocol therapy for patients receiving radiation as part of a primary treatment of carcinoma of the esophagus, stomach, bile ducts, pancreas, or rectum.

Radiation dose to various intraabdominal structures will be calculated and recorded. The organs contoured will vary for each site; however, typically this will include the stomach, small bowel, duodenum (contoured separately from the remainder of the small bowel), liver, colon, rectum, bladder, kidney, heart, lung, and esophagus. If any of these organs is included in any radiation field it will be contoured in its entirety on the CT simulation planning image set and the minimum, maximum, mean, and median dose to this organ will be recorded. In addition, the percentage and volume of this organ receiving above the accepted tolerance dose will be recorded.

3.6 OFF STUDY CRITERIA

3.6.1 *Administrative*

Patients may be taken off study for the following non-medical or administrative reasons:

- Patient refuses the procedure or further treatment
- It is deemed in the patient's best interest as determined by the PI.
- Serious protocol violation as determined by the PI.

3.6.2 *Development of a concurrent serious medical condition that precludes the completion of, radiation therapy or follow-up.*

3.6.3 *Failure to begin radiation therapy or inability to complete a planned course of radiation therapy.*

3.6.4 *The completion of 3 years follow-up.*

3.6.5 *Death*

3.8 POST-STUDY EVALUATION

- Additional blood and/or stool samples may be obtained if deemed necessary by the PI or study chairperson. In these cases, the collection will coincide with regularly scheduled clinic visits.
- The patient should be registered off- protocol by completing the Off Study/ Death Notification Form available from the web site

(http://camp.nci.nih.gov/dcs/rob/rob_index.html) and faxing it to the central registration office at [contact].

4.0 SUPPORTIVE CARE

No supportive care in excess of that required for routine radiation therapy should be required. If patients require supportive care, it will be delivered as per current standard of care. If any anti-fibrotic or immunosuppressive medications are delivered for the primary disease process, side effects, or other disease processes, these will be noted at followup as part of the interval history and physical examination as possible confounding factors.

5.0 DATA COLLECTION AND EVALUATION

5.1 Data Collection

- Research data and acquired samples will be recorded into the CCR database
- Clinical data collection will include: demographic information, pathologic diagnosis, primary tumor site, extent of resection (negative margin, microscopic positive margin, gross positive margin, or biopsy), gastrointestinal function, history including prior therapies, HIV status, sample collection date & time, radiographic evaluations (date & time), radiotherapy details (site, dose, schedule, irradiated volume), concomitant meds & treatments.
- Data from assays run at NIH will be collected in laboratory notebooks and in an electronic database that is shared with the ROB research office..

5.2 Response Criteria

This is not a treatment study and will be administered in conjunction with protocol therapy for patients receiving radiation as part of treatment of their gastrointestinal carcinoma. Response will be assessed according to the patient's primary treatment protocol, as clinically indicated based on their disease site. For consistency in addressing this protocol's objectives, we will use this response information to group patients into the following categories at their follow- up time points (1,3,6,12, 24 & 36 months):

5.2.1 Complete response (CR) is defined as no clinical, radiographic or laboratory evidence of disease following treatment

5.2.2 All other classifications of the RECIST criteria (partial responders, stable disease, and progressive disease) will be considered not a CR.(as defined in 5.2.1). These patients will be considered not complete responders for the purposes of comparison to serum markers.

5.3 Toxicity Criteria

5.3.1 Acute toxicities will be evaluated using the Cancer Therapy and Evaluation Program Common Toxicity Criteria (CTC) Version 3.0 for toxicity and Adverse Event reporting. A copy of the CTC version 3.0 can be down loaded from the CTEP home page (<http://ctep.info.nih.gov>).

5.3.2 Radiation induced gastrointestinal toxicity will be measured with the RTOG and EORTC scoring schemas in Appendices III A and IIIB. These toxicity scores will be correlated with proposed markers of active disease and markers of gastrointestinal toxicity in the serum, plasma, urine, and stool of patients receiving radiotherapy for gastrointestinal malignancies.

5.4 Statistical Section

The two primary objectives are to (i) to examine whether tumor-specific DNA mutations and aberrant DNA methylation at the time of diagnosis and during follow-up is associated with disease persistence, recurrence, or survival, and (ii) whether changes in TGF β 1 in the urine and plasma is associated with late gastrointestinal toxicity. We will discuss analysis and sample size considerations for each primary objective in turn.

5.4.1 Association between tumor-specific DNA markers and subsequent disease.

For the first primary objective, tumor-specific DNA mutation markers will be collected at baseline (before any therapy and before radiation begins) at completion of radiation therapy and at 1, 3, 6, 12, 24, and 36 months of follow-up. Of interest is examining whether changes in the average mutation frequency (of the disease-specific mutations given in Appendix IIA) effects response to therapy, overall survival, and disease-free survival among complete responders to all therapy. Various analyses will be done to address with objective. These analyses will be done separately by tumor type as well as combined over tumor type (assuming that the relationship between marker changes and disease outcome do not vary across tumor type). First, we will examine the relationship between changes in mutational status over time and survival with Cox proportional hazards models. The relationship between changes in mutational status over time and complete response will be estimated using logistic regression analysis. One key primary analysis will be to examine whether having all tumor-specific markers being negative at 3 months after radiation therapy ends is associated with long-term survival. Note that based on the tumor marker prevalences in the literature (see Appendix IIC) and an assumption that marker prevalence is independent across the various markers, the probability of having at least one mutation which is positive before treatment is very high. Our sample size calculations assume that 50% of patients will have all tumor-specific markers negative 3 months after radiation therapy ends. Based on conducting a two-sided log-rank test at the 0.05 significance level with a total enrollment of 120 patients, we would have 89% power to detect a difference between 35% overall 2-year survival in the positive marker group and 65% overall 2-year survival in the negative marker group. We will have power only to detect large differences for the tumor-specific analyses. With 30 patients in each group (15 patients in the positive and negative groups, respectively), we would have 83% power to detect a difference in 2 year survival of between 80% in the marker negative group and 20% in the marker positive group using a log-rank test at the 0.05 significance level. The above sample size calculation depends heavily on the assumption that 50% of patients will have all tumor-specific markers negative at 3 months. The power may be severely diminished if this proportion deviates too much from 50%. Thus, alternative similar analyses will also be conducted. For example, we will compare survival by whether the change in tumor-specific marker frequency from

baseline to 3 months after radiation therapy ends (i.e., difference between proportion of positive markers at 3 months after radiation and proportion at baseline) is above or below the median value. The above sample size calculation also applies to this analysis (e.g., we will have 89% power to detect a difference between 35% overall 2-year survival in the above the median change group and 65% in the below the median change group).

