1.2 BACKGROUND AND RATIONALE

1.2.1 Gastrointestinal carcinoma

Gastrointestinal (GI) carcinomas represent one of the most commonly diagnosed malignancies in the United States¹. Although significant improvements in local control and survival have been achieved in these disease sites over the past several years, locoregional and distant failure remain a significant concern. Radiation plays a prominent role in the definitive management of many GI malignancies, including esophageal cancer, gastric cancer, rectal cancer, and pancreatic cancer. Radiation and chemotherapy are often delivered as adjuvant therapy following resection, as neoadjuvant therapy prior to resection, or as definitive therapy for these malignancies.

Assessment of response to therapy and accurate determination of disease status in gastrointestinal malignancies are complicated by the internal location of the tumors, the resolution of current imaging modalities, and the anatomic distortion introduced with surgery and radiation. When radiation is used as a component of definitive therapy, residual scarring and radiographic abnormalities often persist, making the determination of clinical response difficult. In the case of radiation as a component

of adjuvant therapy after a total resection, treatment is delivered to patients at high risk of local recurrence, often without evidence that residual disease exists. A sensitive and specific marker of tumor persistence or recurrence would permit a more accurate determination of the appropriateness of adjuvant therapy in patients with no clinical evidence of disease following curative resection and allow the diagnosis of recurrences at earlier stages that may be amenable to curative salvage therapies.

Multiple serum markers of malignancy have been explored in the hopes of developing effective screening, assessing response to therapy, and developing prognostic markers. The best studied and clinically useful tumor markers are proteins elaborated in elevated amounts by the tumor tissue, such as Ca 19-9, CEA, AFP, beta-HCG, CA 125, and PSA²⁻⁴. None of these markers is completely specific to tumor tissue, and elevation in the serum levels of these markers may be associated with inflammatory states and other benign disease processes^{3,5-9}.

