3.0 STUDY IMPLEMENTATION

3.1 STUDY DESIGN

3.1.1 Overall Trial Design (see Appendix IA)

Patients planned to receive radiotherapy for carcinoma of the esophagus, stomach, pancreas, rectum, or other biliary malignancies as part of their primary therapy will be potential candidates for enrollment on this protocol. This is not a study of an experimental therapy and will be administered in conjunction with protocol therapy for patients receiving radiation as part of the treatment of a gastrointestinal carcinoma. 120 patients will be included from the following sites: 30 patients with esophageal or GE junction cancer, 30 patients with locally advanced biliary malignancies (including pancreas and bile ducts only), 30 patients with resected biliary malignancies (including pancreas and bile ducts only), and 30 patients with rectal cancer.

Serum, plasma, urine, and stool samples will be collected prior to any therapy (surgery excluding biopsy, systemic therapy, or radiotherapy), prior to radiotherapy (if different from "prior to any therapy"), at completion of radiation (within the final five fractions), and at 1, 3, 6, 12, 24, and 36 months follow-up

The Intestinal Permeability Assessment will be performed following protocol sample collection (above) at the following time points: prior to any therapy, prior to radiotherapy (if different than "prior to therapy"), at 1 month follow-up, and at 3 months follow- up.

Tumor tissue obtained at biopsy or resection will be screened for a defined panel of mutations using PCR and abnormal methylation status will be determined by methylation specific PCR. Serum, urine, and stool samples obtained prior to therapeutic intervention will be screened for the same panel of markers. Serum, urine, and stool obtained during treatment and at follow-up will be evaluated for these

same DNA markers and correlated to evidence of gross residual disease on physical examination and follow-up imaging.

Potential serum, plasma, and stool markers of gastrointestinal toxicity will be correlated to validated measures of gastrointestinal toxicity.

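### The pooled marker analyses in section 5.4.1 name no stratum or group term, so group differences in survival are not separated from the marker effect

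*Combined protocol and SAP*

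**What the plan says.** Section 5.4.1 sets out how the marker data are to be analysed in these terms: "separately by tumor type as well as combined over tumor type (assuming that the relationship between marker changes and disease outcome do not vary". The variation meant is that between tumor types. It then lists a Cox model for survival, a logistic model for complete response, and a key primary comparison of survival by whether all of a patient's markers are negative three months after radiotherapy. The power statement reads: "Based on conducting a two-sided log-rank test at the 0.05 significance level with a total enrollment of 120 patients". It gives 89% power for 35% against 65% two-year survival, with half the patients marker-negative. For single tumor types it concedes: "We will have power only to detect large differences for the tumor-specific analyses". That sentence is backed by 83% power for 20% against 80% ("With 30 patients in each group (15 patients in the positive and negative groups, respectively").

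An alternative analysis splits patients at the median of the "difference between proportion of positive markers at 3 months after radiation and proportion at baseline" and claims the same power.

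None of these analyses names a stratum, a group covariate or any other adjustment. Section 5.4.2, by contrast, names adjustment for radiation dose.

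Section 3.1.1 enrols 30 esophageal or GE junction patients, "30 patients with locally advanced biliary malignancies (including pancreas and bile ducts only), 30 patients with resected biliary malignancies", and 30 rectal patients.

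**The concern.** The assumption in 5.4.1 is that the marker-outcome relationship is the same in every tumor type. A stratified combination needs that assumption. An unstratified test needs more: that group is not associated with both survival and marker status.

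The groups differ by design, and the documents suggest two ways in which the all-negative rate could differ between them.

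- **Residual disease.** Section 1.2.1 says that radiotherapy after total resection is given "often without evidence that residual disease exists". Section 3.4 requires that "protocol enrollment and the initial sample collection must occur prior to initiation of chemotherapy or complete resection", so in the resected group the three-month sample would be expected to follow surgery. If the marker tracks residual disease, that group should be negative more often than the locally advanced group.
- **Number of markers followed.** Appendix IIA gives each site its own panel and carries forward the markers found in the tumor. More markers mean fewer chances of all being negative. This bears on the all-negative comparison only, not on the proportion-based median-change comparison.

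If survival and negativity both differ by group, the pooled test can show an association with no marker effect inside any group, or hide a real one. If only survival differs, type I error holds but the unstratified test can lose power. An unstratified result still describes overall association, but it cannot show that the marker adds anything to the known tumor group.

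**Working it through.** **1. The plan's own figures.** Freedman's formula, exponential survival, deaths expected by two years.

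- Pooled: HR = ln 0.65 / ln 0.35 = 0.410 (inverse 2.44). Deaths = 60 × 0.65 + 60 × 0.35 = 60. Power = Φ(√60 × 0.590/1.410 − 1.96) = 89.9%, against 89% stated.
- Single group: HR = ln 0.80 / ln 0.20 = 0.139. Deaths = 15. Power = 83.4%, against 83% stated.

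Both reproduce. Neither contains a group term.

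**2. Can the by-type analyses stand in for the pooled test?** At the pooled effect (65% against 35%) with 30 patients there are 15 deaths, and Φ(√15 × 0.590/1.410 − 1.96) is about 37%. Simulation gives 39%. No single group can carry the question.

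**3. Simulation set-up.** Four groups of 30, exponential survival, censoring at 24 months, two-sided 0.05. Two-year survival by group is assumed, because the documents give none (esophagus / locally advanced / resected / rectal): mild 45/40/50/60%, moderate 45/20/50/80%, strong 35/10/45/85%. Power figures are good to about one point.

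**4. The plan's own 50:50 split in every group.** Type I error is 4.9-5.2% unstratified. Power at HR 2.44:

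| Survival differences | Unstratified | Stratified |
|---|---|---|
| None | 92.5% | 91.7% |
| Mild | 92% | 92% |
| Moderate | about 85% | about 93% |
| Strong | about 79% | about 94% |

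**5. Negativity derived from the prevalence appendix.** Summing prevalence midpoints over each panel gives the expected number of markers followed:

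- esophageal adenocarcinoma: 0.95 + 0.70 + 0.70 + 0.12 + 0.56 + 0.475 = 3.5
- pancreas: 0.85 + 0.625 + 0.50 + 0.335 + 0.85 = 3.2
- squamous: 0.475 + 0.56 + 0.39 + 0.70 = 2.1
- rectal: 3 × 0.35 + 0.25 + 0.13 + 0.68 = 2.1
- bile duct: 2.0 to 3.2, depending on whether the 83% for p16 and p14 is split between them or applies to each

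Assume that each tumor marker is still detectable at three months with one common chance d, solved so that half of all patients are negative. The all-negative share is the product of (1 − prevalence × d). For rectal with d = 0.218: 0.924³ × 0.946 × 0.972 × 0.852 = 62%.

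Unstratified type I error by histology mix:

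| Mix | Negative by group | Mild | Moderate | Strong |
|---|---|---|---|---|
| All adenocarcinoma and pancreas | 44/47/47/62% | 5.5% | 8.2% | 10.2% |
| 75% | 45/48/48/59% | 5.5% | 7.0% | 8.1% |
| 50:50 | 46/49/49/56% | 5.3% | 5.9% | 6.1% |
| All squamous and bile duct (lower reading) | 48/51/51/49% | 5.1% | 5.3% | 4.9% |

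The mechanism, for the first row with moderate survival: two-year survival among negatives is (0.44×45 + 0.47×20 + 0.47×50 + 0.62×80)/2.00 = 51%. Among positives it is (0.56×45 + 0.53×20 + 0.53×50 + 0.38×80)/2.00 = 46%. That gap of about five points arises with no marker effect in any group.

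**6. Hypothetical shares, moderate survival.** Negativity 50/25/65/60% gives 22% type I error unstratified. In the opposite direction (50/65/50/35%), unstratified power is about 40-48%, depending on how group survival is held fixed when the marker effect is added. Stratified power is about 91%.

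**7. The stratified test.** Its type I error is 4.7-5.6% in all these cases, but each assumes uniform survival within a group. Now let survival and negativity differ by histology inside the groups: survival 30 vs 60%, 10 vs 30% and 35 vs 65% in the esophageal, locally advanced and resected groups, 80% rectal; negativity 37 vs 55% in esophagus and 41 vs 57% in biliary. Type I error is then about 7.6-7.9% stratified, against 10.2% unstratified.

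**The case against.** **The plan is silent, not wrong.** A combined analysis under a common marker effect could be run as a stratified one, and the pooled log-rank appears only in the power calculation. A reader might infer that 5.4.1 prescribes an unstratified test. It does not. This stands, but leaving the choice until the data are seen is what a prespecified key analysis should avoid.

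**The by-type analyses already remove between-type confounding.** They do, and four estimates read together would help. But each is weak at the pooled effect. Locally advanced and resected biliary cancers also share tumor sites, so a split by tumor type need not be a split by enrolment group, although the statement about 30 patients per group suggests that it is.

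**The size rests on assumed inputs.** This stands. A reader might infer from the 22% case that the test is known to be badly anti-conservative. The documents do not support that. Even the direction is open: section 1.2.2.1 reports most success with stool, so rectal markers may be easier to detect. A rectal persistence twice as high reverses the direction of the bias (5.2-13%).

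**Both mechanisms are inferred.** Section 3.1.1 can be read as following the full panel rather than only the tumor's own markers. Patients with no tumor marker have nothing to follow, and excluding them lowers the top figure in step 5 to about 8.7%. No passage states the order of surgery and radiotherapy for the resected group, and section 3.4 allows surgery for any patient. All of this stands.

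**The objectives ask only about association, in a pilot.** An unstratified result does answer that. The precis, however, looks to an individualized method of judging disease status and prognosis, and for that the within-group question matters.

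**Conclusion.** The omission is real, and naming the stratification is a cheap improvement. It is not an error in a stated figure: the 89% reproduces and barely moves under the change when groups are equal.

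The clearest gain needs no confounding. With the plan's own 50:50 split, stratifying recovers about 8 power points under moderate assumed survival differences (85% to 93%) and about 15 under strong ones (79% to 94%). With appendix-based shares, unstratified type I error is about 5-10% and may well be nominal. Larger values come only from hypothetical shares. False positives require survival and negativity both to differ by group.

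A reader might also infer that stratifying by enrolment group removes all confounding. It removes the between-group part only. Squamous against adenocarcinoma, and pancreas against bile duct, are mixed within groups.

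No size is claimed for the median-change or complete-response analyses. Confidence is high that the term is missing and moderate on the size of any bias.

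**What to change.** In section 5.4.1:

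- Stratify the pooled log-rank and Cox analyses, including the median-change comparison, by the four enrolment groups of 3.1.1.
- Assign eligible gastric patients to a stated stratum. Section 2.1.1.2 admits stomach cancer, but 3.1.1 gives it no group.
- Add enrolment group to the pooled complete-response logistic model.
- Keep the by-type and unstratified results as supporting analyses.
- Add a sensitivity analysis with a histology covariate.

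This takes a few sentences and no new data. In simulation, power moves from 92.5% to about 91.7% if groups are equal. With unequal survival and appendix-based shares, stratified power is 91.5-93.9%. If marker shares are strongly unequal (hypothetical 50/25/65/60% or 40/20/70/70%, moderate survival), it is 87.6% or 84.6%, against the stated 89%. The unstratified figures in those two cases (98.8% and 99.8%) are inflated by confounding and are not a fair comparator.
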